Pentoxifylline Treatment in
Acute Pancreatitis: A Double-
Blind Placebo-Controlled
Randomized Trial

NCT 02487225

January 9, 2017

TITLE AND SUMMARY PAGE

Project Title: Pentoxifylline Treatment in Acute Pancreatitis; A Double-Blind Placebo-Controlled Randomized Trial

Principal Investigator:

[name] [name]
Section of Gastroenterology and Hepatology
Professor of Medicine
Mayo Clinic College of Medicine
[name]
[contact]
[contact]
[contact]

Participating Investigators:

[name].
[name].
[name]

Project Summary:

Background. Acute pancreatitis (AP) is a cause of significant morbidity and mortality and effective therapeutic regimens to treat this condition are lacking. Extensive experimental evidence indicates that tumor necrosis factor alpha (TNF- α) contributes to the pathogenesis of multiple organ failure (main cause of morbidity and mortality) in AP, suggesting a possible role for inhibition of TNF- α in the treatment of AP. There is no effective drug therapy for AP and hardly any human experience about the role of pentoxifylline in AP Methods: Randomized, double-blind, placebo-controlled study comparing three times daily dosing with Pentoxifylline from the time of admission until 72 hours of hospitalization in patients presenting with AP. Seventy-five patients will be enrolled in both the "treatment" and "placebo" groups (150 patients total). This study will be performed at Mayo Clinic, Rochester. Primary outcomes: Determine changes in CRP, TNF- α , IL-6, and IL-8 levels from admission baseline at one week.

Significance: If our hypothesis is confirmed this trial will be a landmark development in the treatment of AP. A simple, safe, and inexpensive drug that can be given to all patients with AP, in all settings, will be available to decrease the significant morbidity and mortality due to this disease.

PROJECT DESCRIPTION

Specific Aims:

Aim1: Determine if oral pentoxifylline will improve clinical outcomes in AP. Persistent SIRS and organ failure, pancreatic and/or peripancreatic necrosis and infection (determinants) will be primary endpoints, while death (infrequent), length of stay, and the need for ICU and intervention will be secondary endpoints. These are all identified in the revised Atlanta classification as outcomes of interest. Hypothesis: Pentoxifylline will decrease the occurrence of any one of the following adverse outcomes in AP: pancreatic and/or peripancreatic necrosis and infection, persistent organ failure, prolonged hospital stay, need for ICU, and intervention and death in patients with AP.

Aim2: Determine if oral pentoxifylline will decrease serum levels of inflammatory markers.
Hypothesis: Pentoxifylline will reduce levels of CRP, TNF- α , IL-6, and IL-8, and this reduction will correlate with clinical outcomes in patients with AP.

Background and Significance:

Acute pancreatitis, an inflammation of the pancreas gland, is the most common gastrointestinal hospital discharge diagnosis and averages \$2.6 billion in costs per year. Yet, as common as it is, there is no specific drug to treat this disease. There has been no drug trial in AP since the beginning of this century. Based on previous animal studies and a pilot study in humans at our institution, pentoxifylline has shown to block the inflammation in this disease. A larger study must be performed before the efficacy of this drug can be confirmed. A successful study would provide a breakthrough in AP therapy, paving the way for a simple, safe, and inexpensive drug to be available world-wide to treat this disease. This novel approach would be a major advancement in the treatment of this disease.

Acute pancreatitis (AP) is a common inflammatory condition of the pancreas leading to the hospitalization of millions of patients annually worldwide. While the majority of patients (~80%) have mild, self-limiting disease with low mortality, severe acute pancreatitis (SAP) is associated with high morbidity and mortality (20-40%) and prolonged hospital stays. Specific pharmacological therapies, such as aprotinin, glucagon, gabexate, somatostatin and lexipafant, have not been shown to have any advantage in randomized controlled trials. As a result, treatment for AP is mainly supportive involving bowel rest, aggressive intravenous fluid resuscitation and pain control -a targeted therapy for AP is therefore urgently needed.

Significance

The morbidity, mortality, and increased costs in acute pancreatitis (AP) are mainly due to the more serious forms, moderate and severe, described in the latest revised Atlanta classification(4). The accepted important clinical outcomes of AP include systemic inflammatory response syndrome (SIRS), pancreatic and/or peripancreatic necrosis and infection, persistent organ failure, length of hospital stay, admittance to the intensive care unit (ICU) or intensive care intervention, and death. In our prospective study, 31% of 137 consecutively admitted patients with AP had moderate or severe AP,10 while in another study half of the 619 patients with AP, who had a computed tomography (CT) scan at our institution had such serious disease (unpublished data). Two important reasons for the significant morbidity and mortality seen in AP are the inability to accurately predict these serious forms in the early stages and the absence of an effective drug that could prevent the progression to such serious forms. It is for this reason current guidelines for the treatment of AP, recommend “supportive care” as the main treatment.(2) The many available predictors of severity in AP have reached a plateau for their efficacy(5) and thus there is no reliable way at admission to predict those who will require a drug to prevent the adverse outcomes. Hence, all patients need to be targeted. If all are to be given a drug, it has to be inexpensive, easy to administer, and safe. Pentoxifylline meets all these criteria and can be administered in both academic and community settings. Complicated interventions like intravenous and intra-arterial therapies are not the ideal therapies for this purpose. With this background, it can be clearly appreciated that a simple, safe, and inexpensive drug that could be

administered to all patients diagnosed with AP in academic, as well as in community settings, is urgently needed. Clinical drug intervention trials in AP are conspicuously absent since the negative lexipafant study in 2001.(11) This is due to the inherent difficulties in conducting such trials and the lack of drugs with good efficacy in experimental animals. Extensive animal studies suggest that TNF- α is an important inflammatory mediator in AP.(12-15) TNF- α is the prototypic member of a cytokine family that regulates essential biologic functions such as cell differentiation, proliferation and apoptosis.(9,16) By up-regulating several different genes, such as cytokines, chemokines, NF-kB, cell adhesion molecules, and inducible nitric oxide synthase, TNF- α promotes a proinflammatory action.(17) In AP, TNF- α , IL-6 and IL-8 have been demonstrated to be substantially up-regulated in the pancreatic acinar cells.(17-21) C-reactive protein (CRP) is another inflammatory marker that has been found to be elevated in greater proportion of patients with more serious forms of the disease. Since TNF- α appears to play a central role in the pathogenesis of severe AP, it is possible that inhibition of TNF- α would ameliorate the course of AP.(22,23) Mortality of experimental pancreatitis is dramatically reduced in TNF- α and IL-6 knockout laboratory animals.(24) AP-related complications were ameliorated in rats given anti-TNF antibody.(8,25) Polyclonal blockade of TNF- α significantly reduced the biochemical manifestations of AP and a soluble TNF-receptor antagonist yielded a reduction in the severity and mortality of experimental AP.(26) Pentoxifylline has been used for years in peripheral vascular disease with high degree of safety and is also a TNF- α blocker. It is rapidly and extensively absorbed from the GI tract, peak plasma levels of the drug and active metabolites reach between 2 to 4 hours after a single oral dose of 400 mg extended release form and remain active for extended periods. Hence dosing every 8 hours has been effective for many years for disorders like claudication. Its use in alcoholic hepatitis, another TNF- α mediated inflammatory condition, has been well-established.(27) Human studies in cirrhosis,(28) cardiac surgery,(29) and hemodialysis(30) not only demonstrated its safety with regards to infection, hemorrhagic complications and renal complications but its beneficial effect all with the oral 8 hourly dosing (intravenous form not easily available in the US). We have already demonstrated the capability to successfully complete a clinical trial in AP at our institution due to the factors elaborated in the specific aims section, and the results were encouraging with regards to the safety of pentoxifylline (investigational drug#: 104240) and possible efficacy. We propose this study would validate the efficacy and safety of oral pentoxifylline to decrease the morbidity and mortality and reduce the levels of inflammatory markers in all patients presenting with AP.

Preliminary Results:

We have already successfully conducted a pilot double-blinded, placebo-controlled, allocation-blinded RCT of oral pentoxifylline in patients with AP with any one of several reported predictors of severe disease. By selecting many reported predictors of severity, we attempted to avoid as many patients with a mild form of the disease as possible. Both groups had 14 patients, evenly matched for age and sex; APACHE II and SIRS scores at admission; and pancreatic and/or peri-pancreatic necrosis. Compared to the placebo group, the pentoxifylline group experienced a 29% reduction in length of hospital stay, a 29% reduction in the need for an ICU stay, a 21% reduction in persistent organ failure, and a 7% reduction in pancreatic necrosis or fluid collection. The reductions translated to having no patients with: hospital stays over 10 days, an ICU need, persistent organ failure, interventions, or death in the pentoxifylline group . However, with the small sample size of this pilot study, these clinically significant differences failed to achieve statistical significance except for ICU need. There was no difference in the

inflammatory markers between the two groups over a short period of three days. We concluded that it is feasible to conduct a drug intervention study in a single institution, and pentoxifylline appeared safe and decreased the length of stay and the need for ICU intervention. With larger numbers, besides validating the above findings, we expect to see a beneficial

Experimental Design or Project Summary:

Acute pancreatitis (AP) is an inflammation of the pancreas gland and the most common gastrointestinal discharge diagnosis (approximately 280,000 admissions in 2009). It has resulted in \$2.6 billion, annually, in health care costs, mainly due to the more serious forms of the disease. Lack of any specific drug to treat the condition and predictors to identify patients who will develop more serious forms of the disease contribute to this. Long-term objectives of the study are to find a drug to treat this disease, improve patient outcomes, and reduce the costs of health care. Based on our experience with animals and a small, human subjects pilot study, our hypothesis and specific aims are:

1. Pentoxifylline, administered within 72 hours of diagnosis, improves the clinical outcomes and decreases the occurrence of more serious forms of AP.
2. Pentoxifylline reduces the blood levels of inflammatory markers, which correlates with improvement in clinical outcomes. This study is a novel, exploratory clinical study of the effect of a drug that has a proven role in animal studies in blocking the inflammatory response in AP. It is also a high reward study that will lead to a breakthrough in the treatment of AP and challenge the age old recommendation of supportive treatment alone.

The study will have 2 groups of 75 patients each, all with AP, randomly assigned to either the drug or a placebo, which looks like the drug, for a period of 3 days or until the time they are discharged, if hospital discharge is within 7 days of admission. The levels of markers of inflammation (CRP, IL-6, IL-8 and TNF- α) will be measured at baseline and on 5 successive days or until the time of discharge, whichever occurs earlier. Determination of group size was based on the previous pilot study to decrease any of the important adverse outcomes, providing for a dropout rate of 10% during the study. During 2012, 263 patients with AP were admitted to this institution, which possesses the needed infrastructure for successful completion of clinical drug intervention trials. In the stipulated period of 2 years by the NIH, the required number of patients for the study could be recruited.

This project represents a single center study at Mayo Clinic Rochester. The trial is a randomized, double-blind, placebo-controlled study design.

Subjects: Subjects will be adult patients 18 years of age and greater which will be recruited from Mayo Clinic and admitted to the hospital with acute pancreatitis as defined by at least two of the following:

- amylase and/or lipase greater than 3 times the upper limit of normal values,
- characteristic cross-sectional imaging,
- characteristic pain syndrome.

If patients give consent to be in the study the PI may contact those patients before formally enrolling them in the study. By overseeing that one of the team (a study coordinator, PI, and co-investigator) is present during the weekends, we anticipate that those eligible patients during the weekend period are not going to be excluded.

Patients admitted within 24 hours with AP diagnosis will be included, with the exception of those meeting the exclusion criteria. Those patients that have been identified with AP diagnosis within 72 hours will be approached by the study coordinator and also by the principal investigator (PI) (whenever feasible) to explain the study and obtain written consent.

Inclusion criteria

- Enrollment within 72 hours of diagnosis of AP
- Ability to give informed consent or a legal adult representative LAR able to give informed consent for subject when needed as defined but LAR use guidelines.
- Adult subjects of age ≥ 18 years.

Exclusion Criteria:

- Moderate or severe congestive heart failure,
- History of seizure disorders or demyelinating disease,
- Nursing mothers,
- Pregnancy,
- History of prior tuberculosis or risk factors for tuberculosis
- Evidence of non- corticosteroid immunosuppression (such as malignancy, chronic renal failure, chemotherapy within 60 days, and HIV)
- Evidence of active hemorrhage,
- Paralytic ileus with severe nausea and vomiting.

Laboratory test and assessments:

Test / Procedure	Day 0	Day 1	Day 2	Day 3	Day 4	Day 5
TNF-a*	X	X	X	X	X	X
IL-6*	X	X	X	X	X	X
IL-8*	X	X	X	X	X	X
Pregnancy Test X						
CRP	X*	X*	X*	X*	X*	X*

* Note: The C-RP, TNF-a, IL-6, IL-8 tests are charged to the research study. All other tests listed are clinical standard care for acute pancreatitis.

The pregnancy test may be done as standard of care and will be closely monitored by study staff to assure completion before subject receives study medication.

Follow up process may be done by telephone contact or review of medical records dependant on subjects follow-up information availability. Some subjects may do their follow up visits at a

local facility not return to Mayo Clinic Rochester for follow up visit within the 4 month time frame (plus or minus 15 days). Thus their medical record may not be available in the Mayo Network system. Then a telephone contact may be done to acquire the follow up information.

Randomization:

Randomization will be performed by the pharmacy under the direction of the study statistician, using randomized blocks, to ensure all clinical study personnel are blinded to patient allocation throughout the study. Subjects will be randomized into two groups. The "treatment group" will receive Pentoxifylline 400 mg one to three times daily by mouth from the time of enrollment until 72 hours from enrollment. Subjects will receive up to maximum of 9 doses of this medication. The "control" group will receive placebo dosing at similar intervals. Randomization will occur in a block fashion. Study medication will be administered at 1x/day if creatinine clearance \leq or \geq 30ml/min. per the manufacture prescribing information. All other treatment for AP (fluid resuscitation, antibiotics, surgical intervention, pain control, etc.) will be at the discretion of the primary care team. However, the study investigators will ask primary teams to follow standardized treatment guidelines for acute pancreatitis (to control for intravenous hydration and enteral nutrition, which may influence IL levels).

Blinding: Both subjects and investigators will be blinded to the randomization.

Sample Size:

We propose testing 75 patients in each study arm. Our primary outcome will be whether the patient develops any of the following outcomes of moderate or severe AP: hospital stay longer than 10 days, admittance to the ICU, persistent organ failure, pancreatic and/or peripancreatic necrosis and infection, SIRS, need for intervention, or death. In our pilot study, 7.1% of the patients on pentoxifylline experienced at least one of these outcomes, compared to 28.6% of those on the placebo. If extrapolated to the larger RCT, this reduction in events of these critical outcomes (7.1% vs. 28.6%) would represent a significant and meaningful difference for patients. Using a 5% 2-sided type I error, 58 patients in each group would be needed to achieve 80% power to detect the anticipated difference. In order to account for the unlikely event of up to 10% study dropout, we plan to enroll 64 patients in each group. We will use a randomized block design stratifying for predicted disease severity (mild, moderate, or severe).

Adverse event management: Most of the side effects observed with long clinical use of pentoxifylline are mild and uncommon. Any unexplained hemorrhage of any magnitude will result in stopping the drug. Any of the serious events listed in the drug package insert and informed consent form will result in stopping of the drug if alternative explanation is not found. Adverse events experienced by subject during the study will be evaluated by the investigator. Adverse events will be documented and reported in the IRB annual continuing review. Serious adverse events will be evaluated by both the investigator and found to be related to study then DSMB will be contacted. Serious adverse events will reported according to the FDA and IRB policies and guidelines.

DSMB

For this safety analysis, the study statistician will prepare a blinded assessment of adverse events and severe adverse events by study group. The DSMB, consisting of clinical experts in GI and AP who are not involved in the study will review the blinded report to assess whether they feel either study group is experiencing more adverse events or severe adverse events or more-severe adverse events or severe adverse events. If the DSMB concludes that one group has greater risk, the study statistician will determine whether that group was randomized to pentoxifylline or placebo; if the pentoxifylline group is at risk, the study team will stop enrolling patients and administering the study drug, but will continue to monitor follow-up in previously enrolled patients. DSMB will be constituted by clinicians having experience in TNF- α blockade therapy.

DSMB will receive general updates as well as having contact meeting not less than once a year (per FDA regulation) with either face-to-face, or telephone conference call or e-mail contact. Face-to-face meetings will be conducted as all member schedules allow. If unable to do face-to-face then telephone conferencing or e-mail will be utilized.

Data Collection and Handling: TNF- α , Il-6, and Il-8 will be handled by the research blood draw division of Mayo Clinic per usual practice. The C-RP testing on days 1, 3, 4 and 5 will be handled by the research blood draw division of Mayo Clinic per usual practice. The clinical and research laboratory data will be recorded every day until discharge. Early discharges before completion of 3 days of drug or 5 days of study of markers after drug administration is not considered as protocol violation and data until the time of discharge will be recorded for the purpose of analysis. Data Safety Monitoring Board (DSMB) will be constituted by clinicians having experience in TNF- α blockade therapy.

Data Analysis: All access to data will be password protected. Analysis will be on an-intent-to-treat basis. Outcomes will primarily be descriptive statistics such as means and percents. Continuous secondary end points will be analyzed with the t-test if the data are normally distributed and the Wilcoxon Rank Sum test if non-normal. Analyses of dichotomous secondary end points will use either the Chi-squared test or Fisher's Exact Test comparing proportions. Kaplan-Meier will be used to estimate survival. An interim analysis of data for preliminary review of less than target accrual may be done.

Feasibility: Nearly 250 patients with acute pancreatitis are seen at Mayo Clinic hospitals every year. Assuming ~60% of them are directly admitted to Mayo Clinic (not transferred from outside), and 50% agree to participate in the study it would take 24 months at Mayo to recruit 150 patients. If recruitment goals are not reached at Mayo Clinic after ~24months, the study may have to be extended for 6 months more. **Deliverables:**

We expect to publish at least one manuscript in a major academic journal as a result of this work. Our hope is that any reduction of morbidity or mortality from the novel therapy will have a profound effect on the treatment of acute pancreatitis and lead to future expanded clinical trials.

TAILED MILESTONES SCHEDULE

Endpoints:

May 2015 Mayo Institutional Review Boards (IRB) approval.

June 2015 Approximate NIH will release funds when IRB approved protocol is provided.

July 2015 - Approximate Patient enrollment begins at Mayo

April 2016 Approximate Data Safety Monitoring Board (DSMB) contact via teleconference or E-mail meeting to meet biannually and/or not less-than once a year.

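### No rule says how an in-hospital death enters the length-of-stay comparison, so an early death can count as a short, favourable stay

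*Combined protocol and SAP*

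**What the plan says.** Specific Aims, Aim 1, lists the secondary endpoints separately: "while death (infrequent), length of stay, and the need for ICU and intervention will be secondary endpoints". The hypothesis under the same aim expects pentoxifylline to reduce, among other outcomes, "prolonged hospital stay, need for ICU, and intervention and death in patients with AP".

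Data Analysis gives the methods. "Continuous secondary end points will be analyzed with the t-test if the data are normally distributed and the Wilcoxon Rank Sum test if non-normal". The population is everyone randomised: "Analysis will be on an-intent-to-treat basis". The only time-to-event method is for mortality: "Kaplan-Meier will be used to estimate survival".

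The composite under Sample Size counts a patient as having an event for any of "hospital stay longer than 10 days, admittance to the ICU, persistent organ failure, pancreatic and/or peripancreatic necrosis and infection, SIRS, need for intervention, or death".

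The documents do not define length of stay for a patient who dies in hospital. They give no worst rank, no analysis of time to discharge alive and no sensitivity analysis. They also name no test for length of stay. That it falls under the rule for continuous secondary endpoints is inferred from Aim 1 and Data Analysis read together.

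**The concern.** Length of stay is useful as an outcome because a shorter stay usually means faster recovery. A stay that ends in death breaks that link. If the recorded number of days is analysed, a patient who dies on day 4 scores better than one discharged alive on day 8, under either test. Intention to treat keeps both patients in the comparison.

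The drug is hypothesised to reduce both long stays and deaths. If it prevented early deaths, part of that benefit would appear as a longer average stay on pentoxifylline, and two secondary endpoints could point in opposite directions for a reason that lies in the analysis. Cutting stay at 10 days does not remove the problem, because an early death is still a stay of 10 days or less.

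**Working it through.** **Plan's own figure.** The documents state no figure for the length-of-stay comparison, so there is none to reproduce. The 58 per group under Sample Size concerns the composite and plays no part here.

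**Step 1: how many deaths?** Background and Significance gives about 80% mild disease and 20-40% mortality in severe disease. If every non-mild patient is treated as severe (an upper-end assumption), overall mortality is 0.20 × 0.20 = 4% to 0.20 × 0.40 = 8%. With 75 per arm, that is 0.04 × 75 = 3 to 0.08 × 75 = 6 deaths per arm.

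**Step 2: shift in mean stay.** Suppose there is no drug effect on stay and d more patients die in one arm of n than in the other. Then

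shift = (d / n) × (mean stay those patients would otherwise have had − mean day of death).

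Assumptions not in the documents: deaths occur in patients whose potential stay is log-normal with median 14 days and log SD 0.6, so its mean is 14 × exp(0.6²/2) = 14 × 1.197 = 16.8 days. Death days are uniform over the range shown. With n = 75, a positive value means the arm without deaths looks worse:

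| Days of death | Mean day | 3 vs 0 deaths | 6 vs 0 deaths |
|---|---|---|---|
| 2-7 | 4.5 | 0.04 × 12.3 = +0.49 | 0.08 × 12.3 = +0.98 |
| 2-14 | 8 | 0.04 × 8.8 = +0.35 | 0.08 × 8.8 = +0.70 |
| 2-30 | 16 | 0.04 × 0.8 = +0.03 | 0.08 × 0.8 = +0.06 |
| 10-30 | 20 | 0.04 × (−3.2) = −0.13 | 0.08 × (−3.2) = −0.26 |

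Simulation with 25% of patients at median stay 14 days and 75% at median 5 days agrees. It gave +0.48 and +0.97 day (days 2-7), about +0.3 for 3 vs 0 (days 2-14), +0.05 and +0.04 (days 2-30), and −0.15 and −0.28 (days 10-30). The sign changes once the mean day of death passes the stay those patients would have had, here about 16.8 days.

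**Step 3: effect on the Wilcoxon test.** All results assume no true effect on stay and 75 per arm.

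- Two-sided rejection (nominal 5%), deaths on days 2-7: 6.5-7.8% across separate runs for 3 vs 0, and about 13-14% for 6 vs 0. On days 2-30: 5.2% and 5.1%.
- Significant against pentoxifylline (nominal 2.5%), deaths on days 2-7: 6.2% for 3 vs 0 and 13.4% for 6 vs 0. On days 2-14: 3.6% and 7.1%. On days 2-28: 2.4% and 2.7%.
- Smaller contrasts, all deaths on days 2-7: 1 vs 0 gives 2.8% against pentoxifylline and 6 vs 3 gives 6.1%. For 2 vs 1 or 3 vs 2, the mean shift is about 0.16 day (1/75 × 12.3) and two-sided rejection is 5.1-5.7%.

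**Step 4: with deaths ranked worst.** For deaths on days 2-7, results significant against pentoxifylline fall to 1.3% (3 vs 0) and 0.8% (6 vs 0). Death timing no longer matters, because every in-hospital death gets the same rank.

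**The case against.** The strongest objection is that the direction depends on an assumption about timing. A reader might infer that preventing deaths necessarily makes the drug's stay look longer. The documents do not support that: they give no timing of death, and Background and Significance links severe disease with prolonged stays. If deaths are spread over a month the bias is close to zero, and if they are late it slightly favours the arm with fewer deaths. This stands, and the point is limited to early deaths.

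A reader might also take 3 to 6 deaths per arm as the expected number. It is an upper-end figure. Aim 1 calls death infrequent. Significance and Sample Size distinguish moderate from severe disease, and the 20-40% mortality applies only to severe disease. A contrast of 6 vs 0 is the upper extreme, and small contrasts are close to nominal even when every death is early. This stands too.

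The composite under Sample Size might be thought to share the flaw. It does not, because a death is an event there. Deaths will also be seen as their own secondary endpoint, with Kaplan-Meier survival, so a mortality difference would be visible beside length of stay. That helps interpretation but does not correct the length-of-stay comparison.

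Finally, no test is named for length of stay, and Data Analysis says that reporting will be mainly descriptive. The test is therefore inferred. A descriptive mean carries the same shift, and a 10-day cut still scores an early death as favourable, so the gap does not depend on which reading is right.

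**Conclusion.** The gap is real but small, and it affects one secondary endpoint. On the natural reading of Aim 1 with Data Analysis, an early in-hospital death enters the length-of-stay comparison as a short, favourable stay, which can bias it against the arm with fewer early deaths. The likely size runs from negligible (1 vs 0, or deaths spread over about a month) to about half a day (3 vs 0, all in the first week). One day and about 13% two-sided rejection is the extreme. These figures rest on assumed distributions of stay and assumed death timing. The documents support neither a fixed direction nor a firm size. The composite and the sample size are untouched. A rule is still worth having: neither the number nor the timing of deaths is known in advance, and a rule chosen after unblinding could be chosen by its result.

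**What to change.** Add to Data Analysis, before unblinding: length of stay will be compared between arms by a Wilcoxon rank sum test in which patients who die in hospital receive the worst rank; length of stay in survivors and the number of deaths by arm will be reported descriptively beside it.

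This needs no new data, no more patients and no change to the sample size. The cost is in interpretation: the test compares ranks of a combined stay-and-death outcome, so it gives no difference in mean days, and the survivor summary is not a randomised comparison. Time to discharge alive, with death as a competing event, would also close the gap if the sponsor prefers a time scale.

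### In the available text, the creatinine-clearance rule for once-daily dosing is true of every patient, so it cannot separate one dose a day from three (minor)

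*Combined protocol and SAP*

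**What the plan says.** The Project Summary describes the intervention as "three times daily dosing with Pentoxifylline from the time of admission until 72 hours of hospitalization". The Significance section supports an 8-hourly schedule: "Hence dosing every 8 hours has been effective for many years for disorders like claudication".

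The Randomization section gives the operative instruction. The treatment group "will receive Pentoxifylline 400 mg one to three times daily by mouth from the time of enrollment until 72 hours from enrollment", and "Subjects will receive up to maximum of 9 doses of this medication". It then states when the lower frequency applies: "Study medication will be administered at 1x/day if creatinine clearance \leq or \geq 30ml/min. per the manufacture prescribing information". Placebo follows similar intervals.

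No other place in the document gives a one-way renal threshold or another criterion for choosing between one and three doses a day. The nearest related text is in the Exclusion Criteria: "Evidence of non- corticosteroid immunosuppression (such as malignancy, chronic renal failure, chemotherapy within 60 days, and HIV". This names chronic renal failure as an example of immunosuppression, but it sets no limit on creatinine clearance and does not cover an acute fall in renal function.

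**The concern.** A dose-adjustment rule has to divide patients into two groups. The dosing range in Randomization implies that some patients get one dose a day and others three, and the clearance sentence is the only text that could assign them. As it reads, it puts everyone in the once-daily group. Followed to the letter, it would replace the three-times-daily regimen that the trial sets out to test.

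What is at stake is delivery of the intended regimen. The sentence is an instruction that pharmacy and ward staff must act on, and they cannot act on it without looking up or inferring the direction of the threshold.

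**Working it through.** **Inputs.** Dose 400 mg, treatment period 72 hours, range of one to three doses a day, maximum 9 doses (all from Randomization); three times daily (Project Summary); 8-hourly interval (Significance).

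**Step 1: reproduce the plan's own figure.** Number of doses = doses per day × (72 / 24). Three times daily gives 3 × 3 = 9, and equally 72 / 8 = 9. This matches the stated maximum, so the maximum is what full three-times-daily dosing over 72 hours delivers.

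**Step 2: coverage of the condition.** The set of clearances at or below 30, joined with the set at or above 30, is the set of all clearances. No patient falls outside it.

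**Step 3: what each reading delivers over 72 hours.**

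| Reading | Clearance below 30 ml/min | Clearance above 30 ml/min |
|---|---|---|
| Literal (both signs) | 1 × 3 = 3 doses, 1200 mg | 3 doses, 1200 mg |
| Reduction at low clearance only | 3 doses, 1200 mg | 3 × 3 = 9 doses, 3600 mg |

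That the reduction belongs at low clearance is an assumption drawn from context, because the prescribing information is not in the documents. Whether a value of exactly 30 counts as low also has to come from there.

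**Step 4: size of the conflict.** For a patient above the threshold, the gap between the readings is 9 − 3 = 6 doses, or 3600 − 1200 = 2400 mg, which is 2400 / 3600 = 67% of the three-times-daily amount. For a patient below the threshold the gap is zero. The figure measures the inconsistency in the text. It does not predict what staff would do.

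**Step 5: consistency with the rest of the section.** Only the one-way reading fits all the other statements: some patients on one dose a day, others on three, and a reachable maximum of 9.

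**Separate point: the treatment window.** The Summary ends treatment at 72 hours of hospitalization, and Randomization ends it 72 hours after enrollment. Enrollment is allowed up to 72 hours after diagnosis. If diagnosis coincides with admission (an assumption), a patient enrolled at hour 48 would be treated for 72 − 48 = 24 hours under the Summary, about 3 doses at three times daily, but for 72 hours and 9 doses under Randomization.

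**The case against.** The strongest objection is that the fault may not be in the plan. The two signs appear as raw typesetting codes, which an author would hardly type into a clinical protocol. Symbol handling elsewhere is uneven: dollar amounts carry a stray backslash, while the age criterion shows a clean sign. A source reading less than or equal to 30 could have been garbled. This cannot be settled from the text available, so the finding stays conditional on a look at the source file.

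The context also largely shows the intent. The sentence itself defers to the prescribing information, pharmacy runs the randomization, and the dosing range together with the 9-dose maximum makes sense only if the lower frequency is for a subgroup. This stands, and it limits the practical risk. It does not make the sentence usable as it reads.

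A reader might infer three stronger things that the documents do not support:

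- **That the rule contradicts the 9-dose maximum, or falls outside the stated range.** It does neither. Three doses respect an upper limit of 9, and once daily lies within one to three times daily. The conflict is with the three-times-daily regimen in the Summary.
- **That patients with poor renal function would be overdosed.** Under the literal reading they get the reduced dose, as they do under the sensible one. The literal problem is under-dosing of everyone else. Overdosing would require staff to apply only the upper sign, and nothing points to that. The exclusion of chronic renal failure also narrows the low-clearance group, although acute reductions remain possible.
- **That the trial loses power or is biased.** Placebo is given at similar intervals, so both arms would be handled alike. The Sample Size section works from event proportions and uses no dose figure. The documents do not suggest that staff would follow the literal reading.

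**Conclusion.** The point holds as a minor wording defect in an operative instruction. In the available text, the only rule that assigns dosing frequency is true of every patient. Taken literally, it gives everyone 3 doses (1200 mg), where three-times-daily dosing gives 9 (3600 mg). The maximum of 9 could then never be reached, and the rule cannot divide patients as the dosing range implies.

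Two assumptions carry this conclusion: that the signs in the source file are as they appear here, and that the intended reduction is at low clearance. If the first fails, the main point falls away. The documents do not say how many patients would have a clearance below 30 ml/min, so the number for whom the rule matters cannot be estimated. The window mismatch is real, but it is a separate wording matter and adds no weight to this point.

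**What to change.** Check the signs in the source file first. If they stand, replace the sentence with a one-way rule: study medication once daily (maximum 3 doses) at low creatinine clearance, and three times daily (maximum 9 doses) for all other patients. Confirm against the cited prescribing information whether low means below 30 ml/min or at or below it, and apply the same schedule to placebo.

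As a separate edit, change the treatment window in the Project Summary to the one in Randomization, 72 hours from enrollment.

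The cost is one look at the source file, one sentence in Randomization and one phrase in the Summary. Sample size, blinding and analysis stay as they are.
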